3.6.1 Adverse Events and Serious Adverse Events

Adverse events will be coded with MedDRA version 22.0 or later. Analysis of adverse events will include the type, incidence, severity and relationship to study investigational product summarized by MedDRA System Organ Class (SOC) and Preferred Term (PT), by treatment group as well as MEDI3506 overall. Treatment emergent adverse event is defined as any AE reported after the first IP up to the wash-out of MEDI3506 (5 half-lives: 90 days after the last dose of IP). If an AE is reported the day of the first IP (ie. Day 1) with a missing time, this AE will be considered as treatment emergent. The AEs summaries will include only treatment-emergent AEs (TEAE), i.e., those starting after the first administration of double-blind investigational product. Subjects will be counted once for specific PT or MedDRA SOC when calculating incidence rates. If the same AE Preferred Term occurs multiple times within a subject, the highest severity and level of relationship observed will be reported. Non-treatment-emergent AEs/serious adverse events (SAEs), i.e., those AEs with onset after screening but before the start of double-blind treatment will be presented in the listings. All TEAEs related to dapagliflozin will also be summarized. For subjects testing positive for COVID-19, overall summary of AEs, AEs by PT and SOC, summary of SAEs, AESI and the proportion of asymptomatic subjects will be provided.

3.6.2 Adverse Events of Special Interest

The following AESIs have been defined in the study protocol and will be particularly monitored in this study:

- Serious hypersensitivity, including Type 1 to 4 hypersensitivity reactions, for example, anaphylaxis and severe allergic reactions, and immune complex disease.
- Injection-site reactions.
- Progression of heart failure.
- Serious infections, including opportunistic infections.
- Gastrointestinal adverse reactions.

In addition, Malignancy and COVID-19 disease may also be of interests.

All Treatment-emergent AESIs will be summarized by Special Interest Group and Preferred Term. Programmatic MedDRA search will be done in addition to AESI collected by CRF to ensure a thorough review.

3.6.3 Potential Hy's Law Cases

Cases where a subject shows elevations in liver biochemistry may require further evaluation and occurrences of aspartate transaminase (AST) or alanine transaminase (ALT) $\geq 3 \times$ ULN together with total bilirubin $\geq 2 \times$ ULN may need to be reported as SAEs. The cases of potential Hy's Law cases will be summarized overall, as well as categorized by MedDRA system organ class and preferred term by treatment group.

3.6.4 Deaths and Treatment Discontinuations due to Adverse Events

Death and AEs resulting in permanent discontinuation from the study drug will be summarized by treatment group. The summary includes overall, categorized by MedDRA system organ class, and preferred term.

3.6.5 Clinical Laboratory Evaluation

Haematology, serum chemistry, and urinalysis laboratory evaluations will be performed during the study. The haematology and serum chemistry parameters as well as their changes from baseline and percent changes from baseline will be summarized with descriptive statistics by treatment group. The haematology and serum chemistry results will also be classified as low (below lower limit of reference range), normal (within reference range), or high (above upper limit of reference range). The urinalysis results will be classified as normal or abnormal. The shift from baseline haematology, serum chemistry, and urinalysis results will be summarized by treatment group at each evaluation time.

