3.1.2 Visit Windows

For statistical summaries and analyses by visits, the visits will be mapped based on the actual study days from the first IP dosing date according to the protocol (section 4.2 Table 5 and Table 6) and labelled as Baseline, Day 15, Day 29, Day 57, Day 85, Day 113, Day 141, Day 169, Day 200, and Day 230.

Baseline values will be defined as the last assessment prior to the first administration of study medication (Day 1).

Except the off-treatment visits of the early dropouts (any visit up to including EOT), the visit windows for post-baseline visits will be mapped based on following the table. Any out of window visit will be labelled as unscheduled visit.

Visit (nominal study day)	Visit Window (actual study day)
Baseline ^a	1
Day 15	9-21
Day 29	22-43
Day 57	44-71
Day 85	72-99
Day 113	100-127
Day 141	128-155
Day 169	156-185
Day 200/Follow up	186-215

Visit (nominal study day)	Visit Window (actual study day)
Day 230/Follow up	216-end of study

^aLast assessment prior to first administration of study medication

- If multiple valid assessments fall within the same visit window, the following rules will be applied.
 - If there are two or more valid observations within the same visit window, then the one closest to the scheduled visit will be used in the analysis.
 - If two valid observations are equidistant from the scheduled visit, then the one with the earlier collection date will be used in the analysis.
 - If two valid post-baseline valid observations are collected on the same day, then the one with the earlier collection time will be included in the analysis.
- **For subjects who dropout treatment early**, the follow up visits (any visit after EOT) will be mapped as follows:
 - Determine the last dose visit window based on its actual study day as per the above table. If the last dose was taken up to actual study day 21, then the last dose visit window will be considered as Unscheduled.
 - Any measurement within (\leq) 2 weeks post last dose will be aligned with the last dose visit window.
 - Any measurement beyond ($>$) 2 weeks but within (\leq) 6 weeks post last dose will be aligned with the next protocol scheduled visit window after the last dose visit window. Note: if the last dose visit window is Unscheduled, then the next protocol scheduled visit window should be considered as Day 29.
 - Any measurement beyond ($>$) 6 weeks but within (\leq) 10 weeks post last dose will be mapped as Day 200/Follow up.

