3.4.5 Sensitivity Analyses

The primary endpoint of UACR at Day 169 post baseline time point in Per Protocol Population will be analyzed, as sensitivity analysis, using an analysis of covariance (ANCOVA) adjusting for treatment, baseline log UACR, and randomization stratification factors with last-observation-carried-forward (LOCF) imputation for missing post-baseline measurements. In case the LOCF analysis is needed, some data handling needs to be considered as follows.

Due to two treatment periods, different imputation rules need to be considered for data cut-off at day 85 and all data available beyond day 85,

- If the data at week 12 is missing, the latest respond before week 12 will be carried forward

- If the data at week 24 is missing, the latest response after week 12 will be carried forward

Should be noted that if subject does not have any data after week 12, then that subject will be excluded from the analysis in week 12-24. The data from unscheduled visits will be included together with other available data for endpoint imputation purpose.

Other sensitivity analyses may also be performed.

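### The laboratory shift tables use one value per visit window, chosen by date and not by size, with no worst post-baseline summary; and the SAP does not say that potential Hy's Law cases are counted by arm from laboratory values

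*SAP*

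**What the plan says.** **Laboratory tables.** SAP section 3.6.5 classifies haematology and chemistry as low, normal or high, and urinalysis as normal or abnormal. It then states: "The shift from baseline haematology, serum chemistry, and urinalysis results will be summarized by treatment group at each evaluation time". It also plans by-arm descriptive statistics for haematology and chemistry values and their changes. It names no worst-value or any-time summary.

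**Visit mapping.** Section 3.1.2 sets the scope: "For statistical summaries and analyses by visits, the visits will be mapped based on the actual study days from the first IP dosing date". By-visit laboratory tables fall under it. Where a window holds several valid values, "then the one closest to the scheduled visit will be used in the analysis". For values outside every window: "Any out of window visit will be labelled as unscheduled visit".

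**Early stoppers.** For visits after EOT in subjects who stop treatment early, a value within "2 weeks post last dose will be aligned with the last dose visit window". However, "If the last dose was taken up to actual study day 21, then the last dose visit window will be considered as Unscheduled". Later values from these subjects map to Day 29, Day 200 or Day 230.

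**Potential Hy's Law.** Section 3.6.3 gives a biochemical criterion (AST or ALT at least 3 x ULN together with total bilirubin at least 2 x ULN) and makes SAE reporting of such cases conditional. Cases are to be summarised overall and also "categorized by MedDRA system organ class and preferred term by treatment group".

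**Unscheduled data elsewhere.** For the LOCF efficacy analysis, section 3.4.5 states: "The data from unscheduled visits will be included together with other available data for endpoint imputation purpose". No matching sentence covers laboratory safety.

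**The concern.** Choosing the value nearest the nominal day suits an efficacy time course. For safety laboratories it means that a worse value can be set aside because of the day it was drawn. Extra samples are often drawn because something looked wrong, and the first two weeks after an early stop are the time closest to whatever caused the stop. Section 3.6 makes the safety evaluation descriptive, so these tables carry much of the laboratory assessment by arm. The SAP treats adverse events differently: section 3.6.1 reports the highest severity per subject and counts events to 90 days after last dose.

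For the liver, a case defined by laboratory values has no SOC or PT unless an adverse event was entered. If the only by-arm table is the coded one, a purely biochemical case has no row in it. At stake is whether a reader of the summary tables can see, by arm, how many subjects ever had an abnormal value or met the hepatic criterion.

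**Working it through.** The plan gives no figure on this point to reproduce. The check is to apply the section 3.1.2 rules day by day.

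**Step 1: coverage.** The post-baseline windows are 9-21, 22-43, 44-71, 72-99, 100-127, 128-155, 156-185, 186-215 and 216 to end of study. They are contiguous from Day 9. Only Days 2-8 have no window.

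**Step 2: which value is used.** In a window with nominal day *n*, the value on the day *d* with the smallest |*d* - *n*| is used; ties go to the earlier date. The size of the value plays no part.

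- Illustration: one subject has a normal value on Day 57 and an abnormal one on Day 68. Both lie in window 44-71. |57 - 57| = 0 and |68 - 57| = 11, so Day 57 is used and the shift table shows normal.
- Seven on-treatment windows (Day 15 to Day 169): 13 + 22 + 4 x 28 + 30 = 177 days. Removing one day per window for the routine sample leaves 177 - 7 = 170 days on which an extra sample could fall.

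| Routine sample | Days on which an extra sample is the one used |
|---|---|
| On the nominal day | 0 of 170 |
| 3 days late (assumption) | *n* - 3 to *n* + 2, so 6 per window; 7 x 6 = 42 of 170 (25%) |
| Missing | all, if it is the only value in the window |

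These are shares of calendar days. They are not shares of abnormal values.

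**Step 3: early stoppers.** Let the last dose be on Day *L*, with *L* at most 21, and take a value after EOT on day *d*.

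| *d* - *L* | Mapped to | Example with *L* = 21 |
|---|---|---|
| up to 14 | Unscheduled | to Day 35 |
| 15 to 42 | Day 29 | Days 36-63 |
| 43 to 70 | Day 200 | Days 64-91 |
| over 70 | Day 230 | from Day 92 |

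Only the first two weeks after the last dose lose their analysis visit.

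**Step 4: potential Hy's Law, texts side by side.**

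- The criterion in 3.6.3 is biochemical and carries no visit-window restriction.
- One output is an overall summary. The text does not say whether it is by arm, or whether it is taken from laboratory data or from reported events.
- The other output is by SOC and PT and is expressly by treatment group.
- Section 3.6.4, on deaths and discontinuations, uses *overall* as one part of a by-group summary. That supports reading it the same way in 3.6.3, but does not settle it.

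**The case against.** A reader might infer that all unscheduled safety laboratory values drop out. They do not. From Day 9 every value falls in a window, and an extra sample is used if it is the nearest or the only one. Nor do early stoppers lose all their data: values more than 2 weeks after last dose are mapped, and section 3.1.2 appears to leave visits up to and including EOT on the ordinary table.

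A reader might also infer that Hy's Law counts depend on MedDRA coding. That is one reading. The overall summary needs no PT, and *by treatment group* may govern both parts of the sentence. A subject meeting the criterion on an off-nominal day could be missing from the shift table and still be counted under 3.6.3. It is therefore not shown that a hepatic signal would vanish from all by-arm outputs.

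Other mitigations are real but partial:

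- Section 3.1.1 includes minimum and maximum in descriptive statistics, so the size of an abnormality is not limited to low, normal or high. If those statistics are produced by visit, however, they rest on the same selected values.
- Section 3.1.1 provides listings, but listings give no frequency by arm. The listing of abnormal laboratory values is stated only for the interim analysis (Appendix A 3).
- Table templates sit in the statistical programming plan (section 1), which is not shown. A worst-value table may exist there.

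What stands is that the SAP states no worst-value rule and leaves the source and layout of the Hy's Law count open.

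**Conclusion.** The point holds in a limited form. Followed as written, section 3.6.5 with section 3.1.2 can leave three kinds of value out of the by-arm shift tables: a worse value elsewhere in a window, any value on Days 2-8, and a post-EOT value within 2 weeks of last dose where that dose was taken by Day 21. Section 3.6.3 does not make clear that laboratory-defined cases are counted by arm.

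The document does not support the stronger statement that abnormalities *are* under-reported. The size depends on how often extra samples are drawn, when, and how abnormal they are, and the SAP gives none of this. The 0 and 25% in the working show how the selection rule behaves under stated sampling days; they do not estimate missed events. No claim is made that any arm is affected more than another.

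This is a cheap improvement. It does not touch the primary analysis.

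**What to change.** **Section 3.6.5.** Add a by-arm shift from baseline to the worst post-baseline value per subject, lowest and highest separately (for urinalysis, any abnormal result). Use all records after first dose up to 90 days after last dose, the span that 3.6.1 already uses for adverse events, and include unscheduled and off-window values. Keep the by-visit shift tables.

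**Section 3.6.3.** State that potential Hy's Law cases are derived from all laboratory records with the SAP's own criterion, and counted as n (%) by treatment group whether or not an adverse event was coded. The SOC and PT table can stay as a supplement.

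**Cost.** Some SAP wording and a few extra tables from data already collected. The downside is that subjects sampled more often have more chances of a worst-case abnormality, so the worst-value table should be read beside the by-visit one.

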3.6.6 Other Safety Evaluations

3.6.6.1 Vital Signs

Vital signs including heart (pulse) rate (beats/min), systolic and diastolic blood pressure (mm Hg), temperature (°C), and respiratory rate (breaths/min), as well as the change from baseline for each of those parameters, will be descriptively summarized by treatment group at each time point.

3.6.6.2 Electrocardiogram

Electrocardiogram parameters will be assessed using standard 12-lead electrocardiography. The following electrocardiogram (ECG) parameters as well as the change from baseline for each of those parameters will be reported and descriptively summarized by treatment group at each of the specified time points: Heart rate (beats/min), RR (msec), PR (msec), QRS (msec), and QT (msec) intervals and the QT corrected interval.

The normality/abnormality of the ECG evaluation will be summarized using frequency tables of the number of subjects with a normal/abnormal ECG evaluation at each scheduled visit.

3.6.6.3 Physical Exam

Endpoints of Physical exam, including cardiac exam, will be listed.

3.6.6.4 Other Safety Endpoints

Other safety endpoints, such as left ventricular ejection fraction (LVEF) as measured by echocardiogram and BNP, will be summarized using descriptive statistics at each time point by treatment group.

3.6.7 Data and Safety Monitoring Board

An independent DSMB has been formed to evaluate safety data from concurrently conducted MEDI3506 Phase 2 clinical studies in other indications. The DSMB will have access to data aggregated by treatment group and will be able to review collected study data by treatment while the study is ongoing. The DSMB will review prespecified data periodically to ensure subject safety and make recommendations to the sponsor regarding further conduct of the study. A separate charter will detail the rules, meeting frequency and scope of the responsibilities of the DSMB.

3.7 Immunogenicity

Anti-drug antibody (ADA) analysis will be based on the safety population.

The following ADA category variables will be evaluated:

- ADA prevalence: subjects who are ADA positive at any visit (including baseline)
- Subjects who are ADA positive at baseline only
- Subjects who are ADA positive at baseline and positive post baseline
- Subjects who are ADA positive post-baseline only (treatment-induced ADA)
- Subjects who are persistently positive; persistently positive is defined as at least 2 post-baseline ADA positive measurements (with ≥ 16 weeks apart) or an ADA positive result at the last available assessment
- Proportion of subjects who are transiently positive; transiently positive is defined as at least one post-baseline ADA positive measurement and not fulfilling the conditions for persistently positive.
- Proportion of subjects who are treatment-boosted ADA; treatment-boosted ADA is defined as baseline ADA titer that was boosted to a 4-fold or higher level following drug administration
- ADA incidence (treatment-emergent ADA), defined as the sum of treatment-induced ADA (post-baseline positive only) and treatment-boosted ADA

Summary of ADA responses during the study with number and percentage of participants in each category and ADA titres over time displaying min, Q1, median, Q3 and max, will be provided by treatment group.

If there is a high incidence of ADA, the association of ADA with MEDI3506 pharmacokinetics will be assessed. The effect of ADA on the primary endpoint will be summarized by descriptive analysis in subgroups of TE-ADA+, ADA negative, and TE-ADA-.

Summaries of adverse events will be presented for the on-treatment period by the subgroups of TE-ADA +, ADA negative, TE-ADA-. Summaries will include adverse events (AEs),

serious adverse events (SAEs), causally of AEs and SAEs as assessed by the investigator, and adverse events of special interest.

The relationship between ADA and secondary efficacy endpoints or PD biomarkers may be explored but will be reported outside the CSR.

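### In SAP Section 3.7, one limb of the persistently positive ADA rule can be met on a pre-dose sample, and the persistent and transient rows mix treatment-emergent with unboosted pre-existing ADA

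*SAP*

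**What the plan says.** Section 3.7 sets the analysis set first: "Anti-drug antibody (ADA) analysis will be based on the safety population". Under Table 2 in Section 3.2 that set is every dosed subject of cohorts 2 and 3, so placebo is included. No exclusion of baseline-positive subjects is stated.

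The persistence rule has two limbs:

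- First limb: "persistently positive is defined as at least 2 post-baseline ADA positive measurements (with ≥ 16 weeks apart").
- Second limb: "or an ADA positive result at the last available assessment".

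The complementary rule reads: "transiently positive is defined as at least one post-baseline ADA positive measurement and not fulfilling the conditions for persistently positive".

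The same list has two rows for pre-existing ADA: "Subjects who are ADA positive at baseline only" and "Subjects who are ADA positive at baseline and positive post baseline". Boosting has its own threshold: "treatment-boosted ADA is defined as baseline ADA titer that was boosted to a 4-fold or higher level following drug administration". ADA incidence, which the SAP equates with treatment-emergent ADA, is "defined as the sum of treatment-induced ADA (post-baseline positive only) and treatment-boosted ADA".

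All categories are to be tabulated by treatment group with counts and percentages. The subgroup summaries of the primary endpoint and adverse events (Section 3.7) and of MEDI3506 concentrations (Section 3.8) use three groups: TE-ADA positive, TE-ADA negative and ADA negative. None of them uses persistence.

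**The concern.** There are two separate defects.

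**The second limb admits a pre-dose result.** The first limb and the transient rule both require post-baseline samples; the second limb does not. If the baseline sample is the only one a subject has, it is also the last available one. A positive result then makes the subject persistently positive with no observation after dosing.

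**The two rows do not separate treatment-emergent from pre-existing ADA.** The SAP draws that distinction for ADA incidence and uses it in every ADA subgroup summary, but not in the persistent and transient rules. A subject with a flat titre from baseline onward is TE-ADA negative in the efficacy, safety and PK summaries and persistently positive in the ADA table.

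At stake is whether the ADA table can answer a natural question: of the subjects with a treatment-emergent response, how many had a lasting one?

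**Working it through.** The SAP states no ADA rate, so there is no planned figure to reproduce. The check applies the rules literally to constructed subjects and then shows how the size depends on assumed rates.

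**Step 1. Literal application.** The ADA sampling days are not in the SAP. Days 29, 57, 85, 169 and 230 are assumed for illustration, as is a baseline titre of 40 where positive.

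| Subject | TE-ADA | As written | With both restrictions |
|---|---|---|---|
| A. Baseline 40, flat at 40 throughout | no | persistent | neither |
| B. Baseline 40, no later sample | no | persistent and baseline-only | baseline-only |
| C. Baseline 40, positive at Day 29 only, unboosted | no | transient | neither |
| D. Baseline 40, then negative, 40 again at the last sample | no | persistent | neither |
| E. Baseline negative, positive from Day 57 on | yes (induced) | persistent | persistent |
| F. Baseline 40, boosted to 160 (4-fold) | yes (boosted) | persistent | persistent |

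The restrictions are a TE-ADA condition on both rules and a post-baseline condition on the second limb. Only B depends on the missing post-baseline condition. A, C and D arise from the missing TE-ADA condition, and remain if the second limb is read as post-baseline.

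**Step 2. All patterns.** A baseline-positive, never-boosted subject with five post-baseline samples has 2^5 = 32 possible patterns.

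- Positive at the last sample: 2^4 = 16, all persistent.
- Negative at the last sample but with two positives at least 112 days apart: Day 169 must be positive, with Day 57 (112 days earlier) or Day 29 (140 days earlier). That gives 3 combinations of Days 29 and 57, times 2 for Day 85, or 6, all persistent.
- Persistent: 16 + 6 = 22. Negative throughout: 1. Transient: 32 − 22 − 1 = 9.

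None of the 32 is treatment-emergent. These are counts of patterns, not probabilities.

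**Step 3. What the table reveals.** Take the second limb as post-baseline. Let P and T be the persistent and transient counts, I the ADA incidence count, and U the count positive at baseline and post baseline minus the boosted count (the unboosted carriers still positive after dosing). Every subject with a post-baseline positive is in exactly one of P and T, so P + T = I + U. U can therefore be read off, but not its division between P and T. The TE-ADA positive persistent count is known only to lie between max(0, P − U) and min(P, I).

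**Step 4. Size under assumptions.** Planned numbers from Section 2.2 are 95 + 95 + 95 + 140 = 425 on MEDI3506 and 140 on placebo; all are taken as dosed and sampled. Assumed, not in the SAP: TE-ADA incidence 5%, half of it persistent, giving 425 × 0.05 × 0.5 = 10.6 subjects (2.5%); and 70% of unboosted carriers positive at the last sample. With p the rate of pre-existing unboosted ADA, the added persistent count is N × p × 0.7.

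| p | Added, MEDI3506 | Persistent row, MEDI3506 | Added, placebo |
|---|---|---|---|
| 0% | 0 | 10.6 (2.5%) | 0 |
| 2% | 425 × 0.02 × 0.7 = 5.95 | 16.6 (3.9%) | 2.0 |
| 5% | 425 × 0.05 × 0.7 = 14.9 | 25.5 (6.0%) | 4.9 |
| 10% | 425 × 0.10 × 0.7 = 29.75 | 40.4 (9.5%) | 9.8 |

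**The case against.** The strongest reply is that the rules are coherent on their own denominator. Once the second limb is read as post-baseline, the two rows partition all post-baseline positivity: baseline-and-post-baseline positives plus post-baseline-only positives. Section 3.7 never says that they split ADA incidence. Their names describe serostatus, not cause, and the table that holds them also lists prevalence and baseline-only positivity. The drug-related measure, ADA incidence, is defined separately and clearly. This stands: the missing TE-ADA condition is not a contradiction, and a deliberate count over all ADA-positive subjects is possible, although the SAP does not say so.

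A reader might infer that the SAP reports pre-existing antibody as caused by MEDI3506, or that it overstates persistent immunogenicity 1.6 to 3.8 times (16.6, 25.5 and 40.4 against 10.6). The documents support neither. The SAP makes no causal claim for these rows. The multiples come wholly from assumed rates and from treating 2.5% as the correct figure, which presupposes a TE-ADA denominator that the SAP did not set.

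It is also fair to say that the table exposes the total unboosted component and that the placebo column shows background reactivity. That lets a reader bound the mixing but not resolve it (Step 3).

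The pre-dose case is probably rare, and the wording of the neighbouring rules makes the intention plain. It is still a rule that gives a wrong result as written.

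Finally, the TE-ADA restriction does not remove every trace of pre-existing reactivity. A subject boosted once who returns to the baseline titre and is positive at the last sample stays persistent. Under the SAP's own definition, however, that subject is treatment-emergent.

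**Conclusion.** Two limited points hold.

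- The second limb is wrong as written, because it lets a baseline-positive subject with no later sample be persistently positive and baseline-only at once. Probably few subjects are affected.
- The persistent and transient rows are neither limited to nor split by TE-ADA status. They combine unboosted pre-existing ADA with the response to MEDI3506, and the persistent share of ADA incidence cannot be recovered from the table. This is a gap in reporting, not an inconsistency.

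The effect is confined to these two descriptive rows. ADA incidence and the TE-ADA summaries of the primary endpoint, adverse events and PK do not use them. The size follows the rate of persisting, unboosted pre-existing ADA, which the SAP does not give. Under the assumptions of Step 4 it runs from nothing at p = 0 to about 30 added subjects among 425 at p = 10%. Those figures show sensitivity and are not a forecast.

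**What to change.** In Section 3.7:

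1. Reword the second limb so that it requires a positive result at the last available post-baseline assessment.
2. Report the persistent and transient categories among TE-ADA positive subjects, by either route:
   - restrict both rows to TE-ADA positive subjects; or
   - keep both rows for all subjects with a post-baseline positive, and split each into TE-ADA positive and TE-ADA negative.

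Either way the TE-ADA positive persistent and transient counts add up to ADA incidence. The split also keeps a persistence classification for unboosted baseline-positive subjects, which the restriction drops.

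The cost is two edited definitions and one filter or split in the ADA derivation. The downsides are a possible departure from a standard template and, under the restriction, smaller counts in the two rows.
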